11.1.1 Time-to-event definition

- Progression-Free Survival (PFS) is defined as the duration of time from start of treatment to time of objective disease progression (including initiation of new therapy or death). Median, 2-year and 4-year landmark PFS analysis will be determined.
- Overall survival (OS) is defined as the duration of time from start of treatment to time of death or last follow-up. Median, 2-year and 4-year landmark OS analysis will be determined.
- The duration of response (DOR) for a given participant will be defined as the number of days from the day the criteria are met for ORR to the date that PD or death are objectively documented. If a participant is still responding, then the participant's data will be censored at the last study visit at which a tumor assessment was performed.

12. DATA REPORTING / REGULATORY REQUIREMENTS

Adverse event lists, guidelines, and instructions for AE reporting can be found in Section 7.0 (Adverse Events: List and Reporting Requirements).

12.1 Data Reporting

12.1.1 Method

The Office of Data Quality (ODQ) will collect, manage, and perform quality checks on the data for this study.

12.1.2 Responsibility for Data Submission

Investigative sites within DF/HCC or DF/PCC are responsible for submitting data and/or data forms to the Office of Data Quality (ODQ) in accordance with DF/HCC policies.

12.2 **Data Safety Monitoring**

The DF/HCC Data and Safety Monitoring Committee (DSMC) will review and monitor toxicity and accrual data from this study. The committee is composed of medical oncologists, research nurses, pharmacists and biostatisticians with direct experience in cancer clinical research. Information that raises any questions about participant safety will be addressed with the Overall PI and study team.

The DSMC will review the protocol up to four times a year with the frequency determined by the outcome of previous reviews. Information to be provided to the committee may include: up-to-date participant accrual; current dose level information; DLT information; all grade 2 or higher unexpected adverse events that have been reported; summary of all deaths occurring within 30 days of intervention for Phase I or II protocols; for gene therapy protocols, summary of all deaths while being treated and during active follow-up; any response information; audit results, and a summary provided by the study team. Other information (e.g. scans, laboratory values) will be provided upon request.

12.3 **Multi-Center Guidelines**

- N/a

12.4 **Collaborative Agreements Language**

N/a.

13. STATISTICAL CONSIDERATIONS

This is a single-arm open-label Phase II study to evaluate the safety and efficacy of Ibrutinib combined with Venetoclax (IVEN) in symptomatic, treatment naïve WM patients.

Study treatment for all participants was terminated by the Sponsor-Investigator in March of 2022 due to 4 events of ventricular arrhythmia. As of 4/1/22 all participants were notified and instructed to stop study treatment and accrual was permanently discontinued.

13.1 **Study Design/Endpoints**

The primary endpoint of the current study is:

- To evaluate the rate of VGPR or better of the combination Ibrutinib + Venetoclax (IVEN) in participants with symptomatic, treatment naïve WM, within 24 months of therapy.

13.2 **Sample Size, Accrual Rate and Study Duration**

Following a Fleming’s one step approach, and assuming a null (H0) VGPR or better rate of 25% (based on previous experience on single-agent ibrutinib efficacy in previously untreated patients with WM), and an alternative (H1) VGPR rate of 45%, a total of 50 evaluable patients need to be accrued to show the proposed difference with an alpha (2-sided type I error) of 0.03 and a power (1-beta or type II error) of 87%. Assuming 10% drop out or unevaluable rate, up to 55 participants will be enrolled. If 19 or more participants obtain a VGPR then the combination of ibrutinib and venetoclax warrants further evaluation. If fewer than 19 participants obtain a VGPR, the combination should not continue further evaluation.

Accrual Targets					
Ethnic Category	Sex/Gender				
	Females		Males		Total
Hispanic or Latino	2	+	6	=	8
Not Hispanic or Latino	10	+	32	=	42
Ethnic Category: Total of all participants	12 (A1)	+	38 (B1)	=	50 (C1)
Racial Category					
American Indian or Alaskan Native		+		=	
Asian		+	1	=	1
Black or African American	1	+	1	=	2
Native Hawaiian or other Pacific Islander		+		=	
White	11	+	36	=	42
Racial Category: Total of all participants	12 (A2)	+	38 (B2)	=	50(C2)
	(A1 = A2)		(B1 = B2)		(C1 = C2)

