13.5 Analysis of Primary Endpoint

Continuous variables will be presented as medians and interquartile ranges. Categorical variables will be presented as numbers and proportions. Responses will be defined based on the criteria established by the 6th International Workshop on WM. The outcome of interest will be achievement of VGPR or better at 24 months from treatment initiation. For this study, a VGPR rate of 25% or less will be considered H0, and a VGPR of at least 45% for patients on IVEN will be considered H1. Participants who have completed at least 4 weeks (1 cycle) of n therapy are evaluable. Participants who are evaluable and discontinue protocol therapy for any reason prior to Cycle 2 Day 1 will be considered to be non-responders.

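### Section 13.2 calls the alpha of 0.03 two-sided, but with 50 evaluable patients and a cut-off of 19 it is a one-sided error

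*Combined protocol and SAP*

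**What the plan says.** Section 13.2 (Sample Size, Accrual Rate and Study Duration) describes a single-stage design ("Following a Fleming’s one step approach"), "assuming a null (H0) VGPR or better rate of 25"% and "an alternative (H1) VGPR rate of 45"%. It states that "a total of 50 evaluable patients need to be accrued", with "an alpha (2-sided type I error) of 0.03 and a power (1-beta or type II error) of 87"%.

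The decision rule is a single upper cut-off: "If 19 or more participants obtain a VGPR then the combination of ibrutinib and venetoclax warrants further evaluation". Fewer than 19 means no further evaluation. There is no lower rejection region. On enrolment: "Assuming 10% drop out or unevaluable rate, up to 55 participants will be enrolled".

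Section 13.5 (Analysis of Primary Endpoint) states the hypotheses in one direction, the last clause being the alternative: "a VGPR rate of 25% or less will be considered H0, and a VGPR of at least 45% for patients on IVEN will be considered". Neither it nor Section 13.7.2 names a test, p-value or confidence interval for the primary endpoint, and nothing elsewhere in the document changes or explains the two-sided label.

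**The concern.** A rule with one upper cut-off and a null hypothesis of 25% or less is a one-sided test. Calling its alpha two-sided means one of two things. Either the label is wrong, or the sample size and cut-off were not derived for the stated level. The second would matter more, because the trial would then be underpowered for its claim. The figures have to be recomputed to tell which it is.

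Even if only the label is wrong, it has a consequence. A reader who takes two-sided 0.03 literally will infer an upper-tail error of 0.03 / 2 = 0.015, about half the true value. Because the analysis sections name no test or interval, this label is the only guidance on the level at which the primary result is to be described.

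**Working it through.** **Inputs.** From Section 13.2: p0 = 0.25, p1 = 0.45, n = 50 evaluable, cut-off r = 19, alpha = 0.03 (labelled two-sided), power = 87%. From Section 13.5: H0 is a rate of 25% or less, H1 a rate of at least 45%.

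**Formula.** With X the number reaching VGPR or better, X ~ Binomial(n, p). The upper-tail error is P(X ≥ r | p0) and the power is P(X ≥ r | p1).

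**Step 1: reproduce the plan's figures, n = 50.**

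| Cut-off | P(X ≥ r at 25%) | P(X ≥ r at 45%) |
|---|---|---|
| 18 | 0.0551 | 92.3% |
| **19** | **0.0287** | **87.3%** |
| 20 | 0.0139 | 80.3% |

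At 19 of 50 the upper tail rounds to 0.03 and the power to 87%. Both printed figures are reproduced, with 0.03 as a single tail.

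**Step 2: is 50 with cut-off 19 what a one-sided specification would give?** I searched n = 20 to 79, taking for each n the smallest cut-off with upper tail ≤ 0.03 and requiring power ≥ 87%. The smallest n is 50, with cut-off 19. Sample size, cut-off, alpha and power therefore all follow from one-sided 0.03 and 87%.

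**Step 3: can the two-sided label be right?**

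- Two-sided level of 19 of 50: doubling the tail gives 2 × 0.0287 = 0.0575 (from the unrounded tail), and the minimum-likelihood exact p-value is 0.0481. Neither is 0.03.
- Two-sided 0.03 at n = 50: both conventions reject upward only from 20. The upper tail is then 0.0139 and the power 80.3%.
- Two-sided 0.03 with power ≥ 87% (upper tail ≤ 0.015): the smallest n is 63, with cut-off 24, upper tail 0.0147 and power 89.1%.
- Approximate power at n = 50 under two-sided 0.03: 83.0% (normal), 79.2% (continuity-corrected) and 79.5% (arcsine). Under one-sided 0.03 the same methods give 88.6%, 85.6% and 86.7%, which bracket the stated 87%.

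**Step 4: which interval goes with the rule?** Clopper-Pearson lower limits, to be compared with the 25% null:

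| Result | One-sided 97% lower bound | Lower limit of two-sided 97% interval |
|---|---|---|
| 18 of 50 (no-go) | 23.4% | not needed |
| 19 of 50 (go) | 25.1% | 23.4% |

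The one-sided 97% bound agrees with the rule on both sides of the cut-off. The two-sided 97% interval, which the printed label implies, would still include 25% at 19 of 50, a result that the plan calls a go.

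**Step 5: dependence on the number evaluable.** Keeping the cut-off at 19, error and power are 0.018 and 81.5% at n = 48, and 0.073 and 95.6% at n = 55. The latter requires every one of the 55 enrolled to be evaluable.

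**The case against.** The strongest reply is that nothing operative changes. The rule is explicit, the hypotheses are directional, and anyone applying the protocol reaches the same decision with or without the word. The plan specifies no interval or p-value for the primary endpoint, so the mismatch in Step 4 arises only in an analysis it does not call for. Accrual and treatment stopped in 2022, so the correction cannot affect the conduct of the trial. This is right, and it is why the point is about labelling and not about sizing. It does not make the label correct. The results still have to be reported against this plan, and with no test or interval named, an author is likely to take the level from Section 13.2.

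A second reply is that some crude formula might justify two-sided 0.03. One comes close: a normal approximation using only the null variance gives about 51 patients for two-sided 0.03 and 87% power. But a normal boundary with 0.015 in the upper tail lies at 12.5 + 2.17 × √(50 × 0.25 × 0.75) = 19.14 responders. That means a cut-off of 20, not 19, and exact power of 80.3%. The label is not rescued. That a one-sided design was intended remains an inference, but a strong one, since all four printed numbers then agree.

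Third, the figures at 48 and 55 evaluable say nothing about sidedness and would arise with a correct label too. That is fair. They are given only to show that the stated error and power belong to exactly 50.

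**Conclusion.** The concern holds. The 0.03 in Section 13.2 is a one-sided error (exact 0.0287), and the two-sided label is wrong. Two-sided 0.03 and 87% power cannot both hold for an exact test at 50 patients: the cut-off would be 20 and the power 80.3%, about 7 percentage points lower.

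The effect is limited. The sample size and the cut-off are right for the evident design, and the false-go rate of the written rule is about 3%, the printed value. What is misdescribed is the level of the primary test, and a literal reader would understate its upper-tail error by about half.

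This rests on the exact binomial with p0 = 25%, p1 = 45% and exactly 50 evaluable participants. The documents do not say how many were evaluable when accrual stopped. If the number was not 50, the printed error and power do not describe the trial under either label. The correction should be made, but it does not put the decision rule in doubt.

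**What to change.** In Section 13.2, replace the words describing alpha as a two-sided type I error of 0.03 with: one-sided type I error of 0.03 (exact 0.029). Keep 50 evaluable, the cut-off of 19 and 87% power. Add that the error and power apply at exactly 50 evaluable participants. If a confidence bound is reported with the go decision, use the one-sided 97% lower bound, which agrees with the rule.

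The cost is an edit to one sentence and a short addition. Sample size, cut-off and decision are unchanged. The stated alpha will read slightly less favourably than a two-sided 0.03 did.

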13.7.2 Evaluation of the Primary Efficacy Endpoint

All participants who have completed at least 4 weeks of protocol therapy will be included in the evaluation of primary efficacy endpoint. Each participant should be assigned a response category based on the response criteria in Section 11.1.2.

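### The go/no-go rule is a bare count of 19 that fits a one-sided 0.03 test of 25% only for 47 to 50 evaluable patients, and it was not revisited when accrual stopped

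*Combined protocol and SAP*

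**What the plan says.** Section 13.2 sets up a single-stage Fleming design, "assuming a null (H0) VGPR or better rate of 25" per cent and "an alternative (H1) VGPR rate of 45" per cent. It states that "a total of 50 evaluable patients need to be accrued to show the proposed difference with an alpha (2-sided type I error) of 0.03", with power 87%. On enrolment: "Assuming 10% drop out or unevaluable rate, up to 55 participants will be enrolled". Nineteen or more responders means the combination merits further evaluation. For the other outcome: "If fewer than 19 participants obtain a VGPR, the combination should not continue further evaluation". Neither decision sentence names a denominator.

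The analysis set is defined elsewhere and is not capped at 50. Section 13.7.2: "All participants who have completed at least 4 weeks of protocol therapy will be included in the evaluation of primary efficacy endpoint". Section 13.5 uses the same 4-week criterion and fixes the outcome: "The outcome of interest will be achievement of VGPR or better at 24 months from treatment initiation".

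Section 13 was later edited to record the safety stop: "As of 4/1/22 all participants were notified and instructed to stop study treatment and accrual was permanently discontinued". The 50, the 55 and the 19 below that sentence were left unchanged. The number enrolled or evaluable at the stop is not given.

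**The concern.** A fixed responder count is a valid test only at the sample size it was computed for. Here the plan allows the analysed number to differ from 50 in both directions: upward through the enrolment ceiling of 55, and downward through attrition or, now, the early end of accrual.

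The two directions do different harm. With fewer patients, the same 19 demands a higher observed rate, so a result that clearly excludes 25% can still be declared a failure. With more than 50, the same 19 accepts a lower observed rate, and the false-positive risk exceeds the stated 0.03. The early stop makes the first case the main exposure: read literally, the rule could turn short accrual into a negative verdict on efficacy.

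**Working it through.** **Inputs** (Section 13.2): p0 = 0.25, p1 = 0.45, n = 50 evaluable, cutoff r = 19, alpha 0.03, power 0.87, 10% loss, at most 55 enrolled. The analysed n is not reported, so a range is shown.

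**Formulas.** For X ~ Binomial(n, p): type I error = P(X ≥ r | n, 0.25); power = P(X ≥ r | n, 0.45). The matched cutoff is the smallest r with P(X ≥ r | n, 0.25) ≤ 0.03.

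**Step 1: reproduce the design at n = 50.**
- r = 18: type I error 0.0551
- r = 19: type I error 0.0287, power 0.873
- r = 20: type I error 0.0139, power 0.803

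So 19 of 50 with 87% power is the exact one-sided 0.03 design. The label on alpha is two-sided, but an upper tail of 0.015 would require 20 of 50, with power 0.80. The stated figures therefore come from a one-sided test.

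**Step 2: hold the cutoff at 19 and vary n.** The last column is the chance, at a true rate of 45%, of a result that rejects 25% at 0.03 yet is declared a no-go: P(matched r ≤ X ≤ 18 | n, 0.45).

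| n | Type I error, r = 19 | Power, r = 19 | Matched r | Power, matched r | Rejects 25% but no-go |
|---|---|---|---|---|---|
| 30 | <0.0001 | 0.03 | 13 | 0.64 | 0.61 |
| 35 | 0.0002 | 0.17 | 15 | 0.66 | 0.49 |
| 40 | 0.0017 | 0.43 | 16 | 0.79 | 0.35 |
| 45 | 0.0085 | 0.70 | 18 | 0.79 | 0.10 |
| 46 | 0.0111 | 0.74 | 18 | 0.83 | 0.09 |
| 47 | 0.0144 | 0.78 | 19 | 0.78 | 0 |
| 50 | 0.0287 | 0.87 | 19 | 0.87 | 0 |
| 51 | 0.0353 | 0.90 | 20 | 0.83 | not applicable |
| 55 | 0.0729 | 0.96 | 21 | 0.88 | not applicable |

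The matched cutoff is 18 for n = 44 to 46, 19 for n = 47 to 50 and 20 for n = 51 to 53. The type I error of the fixed 19 at n = 52, 53 and 54 is 0.043, 0.052 and 0.062.

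**Step 3: one worked case each way.**
- 18 of 40 = 45%, exactly the alternative. P(X ≥ 18 | 40, 0.25) = 0.0047; Clopper-Pearson 95% interval 29% to 62%. Verdict under the written rule: no-go.
- 19 of 55 = 34.5%. P(X ≥ 19 | 55, 0.25) = 0.073. Verdict under the written rule: go.

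**Step 4: the rule as first planned.** Assume all 55 are enrolled and each is evaluable with probability 0.9, so n ~ Binomial(55, 0.9). Then P(n ≤ 46) = 0.09, P(47 to 50) = 0.56 and P(n ≥ 51) = 0.35. Averaged over n, the fixed 19 has type I error 0.028 and power 0.850. A cutoff matched to n has 0.022 and 0.840.

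**The case against.** The strongest reply has four parts.

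First, the 50 stands in the same paragraph as the 19, so a sensible reader takes the rule as 19 of 50. That is fair, and the design is sound at 50. What is missing is any instruction for another number, which the analysis-set definition and the ceiling of 55 make possible.

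Second, no actual mismatch can be shown, because the analysed number is not in the documents. This also stands. If it was 47 to 49, the cutoff is still right and only power falls (0.78 to 0.85). The gap in the rule exists whatever the number; its numerical effect depends on it.

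Third, as planned the count was close to calibrated on average (step 4), and below 47 it is conservative, with no inflation of false positives. Agreed, which is why the early stop is the main concern. The average does not protect the single trial that was run.

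Fourth, treatment ended for ventricular arrhythmias, so further development is unlikely to turn on 18 versus 19 responders. That may be so. But the primary endpoint and both decision sentences remain in the current Section 13, follow-up continues (Section 1.1) and results are to be published (Section 14). An efficacy verdict should not be a by-product of when accrual ended.

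The 47-to-50 band assumes exact tails and a one-sided 0.03. With 0.015 in the upper tail, 19 would fit n = 45 to 47 and not 50. With a one-sided normal approximation it would fit 50 to 52. On any of these readings, 19 fits only a narrow range of n.

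**Conclusion.** The concern holds. The rule as written is correct for 47 to 50 evaluable patients and gives the wrong verdict for some results at other sizes the plan allows. At n = 40 and a true rate of 45%, about one trial in three (0.35) would reject 25% at 0.03 and still be called a no-go; at n = 30 the figure is 0.61. At n = 51 to 55 the type I error is 0.035 to 0.073 against a stated 0.03. These figures rest on exact binomial tails, on 0.03 read as one-sided (which reproduces 19, 50 and 87% together), and on a true rate of 45%, which presumes full exposure. The analysed number is unknown, so the table shows a range of possibilities and not what happened. The point should be fixed before the primary result is reported; it does not undermine the original design at 50.

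**What to change.** Amend Section 13.2 as follows.

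1. State that 19 applies to 50 evaluable patients.
2. For any other analysed number, decide by an exact one-sided binomial test of 25% at 0.03, and replace the two-sided label on alpha.
3. Give the matching cutoffs: n = 20–22: 10; 23–25: 11; 26–28: 12; 29–31: 13; 32–34: 14; 35–37: 15; 38–40: 16; 41–43: 17; 44–46: 18; 47–50: 19; 51–53: 20; 54–55: 21. The same formula applies below 20.
4. Make the rate of VGPR or better with its exact 95% interval the main result, and restate power for the realised number. The interval uses 0.025 per tail, so at the boundary it can include 25% when the test rejects (19 of 50, p = 0.0287).
5. Label any cutoff other than 19 as set after accrual stopped in an open-label trial.
6. Note that participants on therapy at the stop did not complete 24 cycles. If this lowers the true rate to 40% or 35% (assumed values), power with the matched cutoff at n = 40 is 0.56 or 0.31, against 0.79 at 45%.

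Because one patient moves the cutoff at 46/47 and at 50/51, the analysed number must be fixed first. Section 11.1.1 defines evaluability somewhat differently from Sections 13.5 and 13.7.2, and that separate point needs settling too.

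The cost is SAP wording, a short table and a post hoc label, with no new data. The price is power: 0.79 at n = 40 and 0.64 at n = 30 even with the matched cutoff, and 0.83 instead of 0.90 at n = 51.

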13.3 Stratification Factors

N/a.

13.4 Interim Monitoring Plan

N/a.

13.5 Analysis of Primary Endpoint

Continuous variables will be presented as medians and interquartile ranges. Categorical variables will be presented as numbers and proportions. Responses will be defined based on the criteria established by the 6th International Workshop on WM. The outcome of interest will be achievement of VGPR or better at 24 months from treatment initiation. For this study, a VGPR rate of 25% or less will be considered H0, and a VGPR of at least 45% for patients on IVEN will be considered H1. Participants who have completed at least 4 weeks (1 cycle) of n therapy are evaluable. Participants who are evaluable and discontinue protocol therapy for any reason prior to Cycle 2 Day 1 will be considered to be non-responders.

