11.1 Antitumor Effect – Hematologic Tumors

11.1.1 Definitions

Evaluable for toxicity: All participants who receive at least one dose of study treatment will be evaluable for toxicity from the time of their first treatment.

Evaluable for response: Only those participants who have measurable disease present at baseline, have received at least one cycle of therapy, and have had their disease re-evaluated will be considered evaluable for response. These participants will have their response classified according to the definitions stated below. (Note: Participants who exhibit objective disease progression or die prior to the end of cycle 1 will also be considered evaluable.)

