13.7 Reporting and Exclusions

13.7.1 Evaluation of Toxicity

All participants who receive at least one dose of any test material during the study will be included in the safety analysis.

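### Sections 11.1.1, 13.5 and 13.7.2 give two conflicting rules for the primary efficacy set, and dosed participants who stop in cycle 1 for toxicity or withdrawal meet neither

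*Combined protocol and SAP*

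**What the plan says.** Three places in the combined protocol and SAP define who is counted for response.

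- **Section 11.1.1 (Definitions).** Participants with measurable disease at baseline who "have received at least one cycle of therapy, and have had their disease re-evaluated will be considered evaluable for response". A note adds an exception: "Participants who exhibit objective disease progression or die prior to the end of cycle 1 will also be considered evaluable".
- **Section 13.5.** "Participants who have completed at least 4 weeks (1 cycle) of n therapy are evaluable". The next sentence reads: "Participants who are evaluable and discontinue protocol therapy for any reason prior to Cycle 2 Day 1 will be considered to be non-responders".
- **Section 13.7.2.** "All participants who have completed at least 4 weeks of protocol therapy will be included in the evaluation of primary efficacy endpoint".

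The safety set in Section 13.7.1 is wider: "All participants who receive at least one dose of any test material during the study will be included in the safety analysis". No section applies that set to the primary endpoint.

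Section 13.2 sizes the trial on an evaluable count: "a total of 50 evaluable patients need to be accrued to show the proposed difference". It adds: "Assuming 10% drop out or unevaluable rate, up to 55 participants will be enrolled". The success rule is at least 19 responders, with 25% as the null rate and 45% as the alternative. Sections 5.1 and 13 record that study treatment was terminated and accrual permanently discontinued. No final enrolment is given.

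**The concern.** The primary endpoint is a proportion, so its denominator has to be fixed before the results are known. Here a cycle-1 death or progression is in the denominator under one section and does not meet the criterion of the other two. A participant who completes 4 weeks but is never re-evaluated is treated the opposite way. A dosed participant who stops in cycle 1 because of toxicity or withdrawal is covered by none of them.

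Participants lost this early are very unlikely to have reached a VGPR. Section 11 also bars IgM values measured within cycles 1 and 2 from response determination. Leaving these participants out would therefore tend to raise the reported rate. The trial is single-arm and open-label, so two usable definitions also leave room to choose a denominator after the outcomes have been seen.

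**Working it through.** **Step 1. Apply each rule to the same participant.**

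| Participant | 11.1.1 | 13.5 and 13.7.2 (4-week criterion) |
|---|---|---|
| Dies or progresses in week 2 | Evaluable (exception) | Criterion not met |
| Completes 4 weeks, never re-evaluated | Not evaluable | In the set |
| Stops in week 2 for toxicity or withdrawal | Not evaluable | Criterion not met |

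Sections 13.5 and 13.7.2 share one criterion, so there are two rules in conflict, not three.

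**Step 2. What the non-responder sentence in 13.5 reaches.** It applies to participants who are already evaluable.

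- If evaluable has the 13.5 meaning, the sentence covers those who complete 4 weeks but do not start Cycle 2. This can happen: a cycle may run 4 weeks +/- 1 week (Section 5.3.2), and Day 1 criteria must be met (Section 5.2).
- If evaluable has the 11.1.1 meaning, the sentence also covers cycle-1 deaths and progressions.
- On neither meaning does it cover a cycle-1 stop for toxicity or withdrawal.

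**Step 3. Reproduce the design in 13.2.** Inputs from that section: N = 50, cut-off 19, rates 0.25 and 0.45. With X binomial:

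- P(X ≥ 19 | 50, 0.25) = 0.0287
- P(X ≥ 19 | 50, 0.45) = 0.8727

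Power matches the stated 87%. The stated alpha of 0.03 is reproduced only as a one-sided figure, although 13.2 labels it two-sided. Doubled, it is 2 × 0.0287 = 0.0575 from the unrounded tail.

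**Step 4. Effect on the reported rate.** The number of cycle-1 exits is not in the documents. I assume k = 0 to 5; five is the whole gap between 50 and 55. Taking a boundary result of 19 responders among 50 evaluable and restoring k non-responders gives 19/(50 + k):

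| k | 0 | 1 | 2 | 3 | 4 | 5 |
|---|---|---|---|---|---|---|
| Rate | 38.0% | 37.3% | 36.5% | 35.8% | 35.2% | 34.5% |

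The exact 95% interval is 24.7% to 52.8% for 19/50 and 22.2% to 48.6% for 19/55.

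**Step 5. The cut-off belongs to its denominator.** If all 55 were analysed with 19 still the cut-off, P(X ≥ 19 | 55, 0.25) = 0.0729, against 0.0287 at 50.

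**The case against.** **An evaluable set was planned.** Section 13.2 counts evaluable patients and allows for unevaluable ones. Cycle 1 is ibrutinib alone and the primary objective concerns the combination, so a set of those who finished the lead-in can be defended. That is a fair choice of target population, but the protocol does not give this reason. Section 13.5 also counts some participants who never start venetoclax as non-responders, and 11.1.1 admits cycle-1 deaths and progressions.

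**The sections can be read together.** A reader might infer that 13.5 and 13.7.2 shut out every cycle-1 failure. The text does not go that far. Both say that those who complete 4 weeks count; neither says that nobody else does. Read with the 11.1.1 definition, the non-responder sentence does catch cycle-1 deaths and progressions. This stands, and it limits the point: for those participants the plan is ambiguous, not plainly exclusionary. The toxicity and withdrawal gap remains on either reading.

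**The harm is not shown.** A reader might infer a demonstrated bias or an inflated error rate. The documents support neither. They report no cycle-1 exits, and Section 2.3 describes ibrutinib alone as well tolerated in 30 untreated patients. If the number dosed is fixed, leaving out non-responders does not change whether 19 is reached. The one-sided error of the 19/50 rule would rise to 0.0348 with one excluded, or 0.0694 with five, only on two conditions: extra participants are dosed to reach 50 evaluable, and the 25% null applies to all treated (evaluable null = 0.25 × (50 + k)/50). If 25% is a rate among evaluable participants, the error stays at 0.0287. Section 13.2 does not say which it is.

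**Changing the set now is itself post hoc.** True, and it is a real cost. But the present text already forces a choice between two rules, and the all-dosed set tends to lower the rate.

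**Conclusion.** The inconsistency is certain on the text: two rules for one primary denominator, with cycle-1 toxicity and withdrawal exits meeting neither. The likely direction of bias is upward, because such participants are very unlikely to have a VGPR. The size is unknown and may be small or nil. On the assumption of one to five exits around a boundary result, it is 0.7 to 3.5 percentage points (38.0 − 37.3 and 38.0 − 34.5). Those figures assume 50 evaluable; because accrual stopped early, the actual denominator may differ. With fewer participants, each exclusion would weigh more. The point warrants correction before the primary analysis, but it is not evidence that the reported rate is wrong.

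**What to change.** - Use one primary efficacy set in 11.1.1, 13.5 and 13.7.2: every participant who received at least one dose, as already defined in 13.7.1. Count anyone without a documented VGPR or better as a non-responder, including cycle-1 deaths, progressions and discontinuations.
- Keep the 4-week set as a sensitivity analysis, and report how many dosed participants it leaves out and why.
- State in 13.2 that the cut-off of 19 belongs to a denominator of 50. Report the exact test against 25% and an exact confidence interval at the actual denominator. Correct or explain the two-sided label on the 0.03.
- Date and document the change before the primary analysis.

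The cost is wording in four sections; no new data are needed. The downsides are a slightly lower reported rate, inclusion of participants who never received venetoclax, and a change of denominator after accrual closed, which dating and documenting reduces but does not remove. Simply copying the 11.1.1 exception into 13.5 and 13.7.2 would be a smaller change. It would settle deaths and progressions but leave toxicity and withdrawal exits unclassified.
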